5.3 Categorising comorbidity activity and severity

Many of the comorbidities can be further characterised as inactive or active, and mild or moderate/severe at the index date using prescribing and primary and secondary consultation data. A comorbidity will be defined as inactive in the year prior to the index date if it was not classified as active. Similarly, a comorbidity will be defined as mild in the year prior to the index date if it was not classified as moderate/severe.

Following a rapid review of the definitions applied by studies using routine patient data and prescribing guidelines, the following definitions were adopted.

Note on medications with more than one indication

The indication for a prescription may not be recorded as the time it is issued and some medications can be indicated for more than one of the comorbidities of interest. Following a review of the approaches used in other published studies, the diagnosis recorded closest in time to the initiation of the medication will be taken as the indication. Similarly, the reason for outpatient consultations is not routinely coded in HES data and individual hospital specialties may treat more than one of the comorbidities of interest (e.g. ENT treating both allergic rhinitis and chronic rhinosinusitis). Where this occurs we will attribute the outpatient consultation to the diagnosis recorded closest in time to the secondary care consultation.

Atopic dermatitis

Active: A primary or secondary care consultation in the previous year. Prescription of a topical corticosteroid in the previous year.

Moderate/severe: A primary or secondary care consultation in the previous year. Prescription of a medium- to high-potency topical corticosteroid in the previous year (see Appendix 6 for categorisation of topical corticosteroid preparations).

Allergic Rhinitis

Active: A primary or secondary care consultation in the previous year. Prescription of a nasal corticosteroid in the previous year.

Moderate/severe: A primary or secondary care consultation in the previous year. Three or more nasal corticosteroid in the previous year.

Chronic Rhinosinutis

Active: Always active as this is a chronic condition.

Moderate/severe: A primary or secondary care consultation in the previous year. Three or more nasal corticosteroid prescriptions in the previous year.

Nasal polyps

Active: Always active.

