13.5 Appendix 5: Algorithm to define acute versus chronic oral corticosteroid prescriptions

13.6 Appendix 6: Classification of topical steroid potency

Potency	Class	Topical corticosteroid	Formulation	
Ultra-high	I	Clobetasol propionate	Cream, 0.05%	
		Diflorasone diacetate	Ointment, 0.05%	
High	II	Amcinonide	Ointment, 0.1%	
		Betamethasone dipropionate	Ointment, 0.05%	
		Desoximetasone	Cream or ointment, 0.025%	
	III	Fluocinonide	Cream, ointment or gel, 0.05%	
		Halcinonide	Cream, 0.1%	
		Betamethasone dipropionate	Cream, 0.05%	
Moderate	III	Betamethasone valerate	Ointment, 0.1%	
		Diflorasone diacetate	Cream, 0.05%	
		Triamcinolone acetonide	Ointment, 0.1%	
	IV	Desoximetasone	Cream, 0.05%	
		Fluocinolone acetonide	Ointment, 0.025%	
		Fludroxycortide	Ointment, 0.05%	
		Hydrocortisone valerate	Ointment, 0.2%	
		Triamcinolone acetonide	Cream, 0.1%	
		V	Betamethasone dipropionate	Lotion, 0.02%
			Betamethasone valerate	Cream, 0.1%
Fluocinolone acetonide	Cream, 0.025%			
Low	VI	Fludroxycortide	Cream, 0.05%	
		Hydrocortisone butyrate	Cream, 0.1%	
		Hydrocortisone valerate	Cream, 0.2%	
	VII	Triamcinolone acetonide	Lotion, 0.1%	
		Betamethasone valerate	Lotion, 0.05%	
		Desonide	Cream, 0.05%	
		Fluocinolone acetonide	Solution, 0.01%	
		Dexamethasone sodium phosphate	Cream, 0.1%	
		Hydrocortisone acetate	Cream, 1%	
		Methylprednisolone acetate	Cream, 0.25%	

Source: WHO Model Prescribing Information: Drugs used in Skin Disease. WHO: Geneva, Switzerland, 1997.

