- **Eczema:** Chronic eczema may be defined as having one or more Read codes for eczema separated by between 90 and 365 days or at least one course of a potent topical steroid. Steroid-refractory chronic eczema may be defined as having a dermatology referral or being prescribed phototherapy, systemic immunomodulators, oral corticosteroids, alitretinoin or acitretin.
- **Chronic rhinosinusitis:** Chronic rhinosinusitis refractory to medical management may be defined as having endoscopic sinus surgery.

Results

The full references for the papers identified as relevant and not relevant are listed in Appendix 4-5.

49 potentially relevant papers were identified. 43 papers were categorised as not relevant as they did not provide a definition of disease severity based on their title, abstract or full-text.

Full-text PDFs were found for 4 of the 5 relevant papers. Two were on anaphylaxis, and there was one each on allergic rhinitis, hand eczema and chronic rhinosinusitis.

1. Diwakar, L., et al. (2017).

Anaphylaxis: Patients were defined as at high risk of anaphylaxis in a study year if they had a prescription for an adrenaline autoinjector in that year. Only half of children prescribed an autoinjector had a relevant Read code for allergy or anaphylaxis. (Data source: THIN)

2. Peng, M. M. and H. Jick (2004).

Anaphylaxis: Cases were identified by Read code and free-text comments. Copies of letters from hospital were requested and reviewed. Anaphylaxis was categorised as mild if was primarily limited to generalised urticaria (angioedema) and did not lead to an emergency department admission or hospitalisation. The illness was categorised as moderate severity if a hospital visit was initiated and the illness was treated with adrenalin. The illness was considered to be severe if there was hypotension or shock that was described as life-threatening. (Data source: GPRD)

3. Price, D. B., et al. (2016).

Allergic rhinitis: The paper reported that intranasal steroids are recommended for moderate to severe allergic rhinitis (Allergic Rhinitis and its Impact on Asthma (ARIA) Guideline). (Data source: OPCRd)

4. Crane, M. M., et al. (2017).

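### The atopic dermatitis severity criterion stops at high potency although Appendix 6 has an Ultra-high tier above it, so as written some ultra-high-only patients rank below comparable high-potency patients

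*Protocol*

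**What the plan says.** Under atopic dermatitis, Protocol Section 5.3 gives two statements for moderate/severe disease with no connector between them. The first is a consultation during the year, in either care setting. The second is "Prescription of a medium- to high-potency topical corticosteroid in the previous year". For the grading it adds a pointer: "see Appendix 6 for categorisation of topical corticosteroid preparations".

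Appendix 6 (Section 13.6) has four potency labels: Ultra-high, High, Moderate and Low. The Ultra-high tier contains "Clobetasol propionate" cream 0.05% and diflorasone diacetate ointment 0.05%. The list names individual products by formulation and strength, and its stated source is a 1997 publication, "WHO Model Prescribing Information: Drugs used in Skin Disease".

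A residual rule at the start of Section 5.3 covers the rest: "a comorbidity will be defined as mild in the year prior to the index date if it was not classified as moderate/severe".

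The criterion for active disease has no potency limit: "Prescription of a topical corticosteroid in the previous year".

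**The concern.** The range in Section 5.3 and the labels in Appendix 6 do not match at either end. The lower end uses a word that is not an Appendix 6 label; Moderate is the obvious counterpart. The upper end stops at High, one tier below the top. A programmer who maps products to Appendix 6 labels and then applies Section 5.3 literally would leave Ultra-high products out of the qualifying set, and the residual rule would then apply to them.

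A severity scale built on treatment potency should not fall as potency rises. Here it can. The classification is used in Phase 2: Section 6.4 tabulates mild and moderate/severe numbers for each comorbidity, and Section 6.6 describes each selected cluster by comorbidity severity and activity. Section 5.3 presents the definitions as adopted, so the protocol itself fixes this rule.

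**Working it through.** The protocol states no figure to reproduce. The check applies the written rule to every case.

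**Inputs.** Potency of the only topical steroid prescribed in the year (Appendix 6). Consultation in the year, yes or no (Section 5.3). The missing connector, read as AND or as OR. The residual mild rule (Section 5.3). 'Medium' is taken to mean the Moderate tier.

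**Rule.** Under AND, moderate/severe = consultation and qualifying potency. Under OR, moderate/severe = consultation or qualifying potency. Otherwise mild. On the literal reading the qualifying tiers are Moderate and High.

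| Connector | Consultation | Moderate or High only | Ultra-high only | Low only |
|---|---|---|---|---|
| AND | yes | moderate/severe | mild | mild |
| AND | no | mild | mild | mild |
| OR | yes | moderate/severe | moderate/severe | moderate/severe |
| OR | no | moderate/severe | mild | mild |

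**Results.**

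1. The Ultra-high-only patient is mild in 3 of 4 cells, and gets the same class as the Low-only patient in all 4.
2. The order against High is inverted in 2 of 4 cells: AND with a consultation, and OR without one. Each reading of the connector has one such cell, so settling the connector alone does not remove the fault.
3. In the other two cells potency makes no difference: AND without a consultation is mild throughout, and OR with a consultation is moderate/severe throughout.

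**Example from Appendix 6.** Diflorasone diacetate 0.05% ointment is Ultra-high and fails the potency criterion. Diflorasone diacetate 0.05% cream meets it. The tier boundaries in the extracted table are broken, but the cream falls in High or Moderate on either reading, and both qualify. The same drug at the same strength thus gets the lower severity class in the formulation that Appendix 6 ranks as more potent.

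**Who escapes.** The rule needs only one qualifying prescription in the year. A patient with an Ultra-high product and also a Moderate or High product meets it.

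**Size.** The share affected would be the proportion of atopic dermatitis patients whose only topical steroid in the year is Ultra-high and who fall in an inverted cell. The protocol gives no prescribing frequencies by potency and no consultation rate, so this cannot be calculated. Section 6.1 gives only the numbers of asthma patients available.

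**The case against.** The strongest reply is that this reads the phrase too literally. Section 5.3 is not quoting tier names, since Appendix 6 has no medium tier. In a split between mild and moderate/severe, the natural meaning may be anything above low. The protocol's own rapid review (Appendix 13) points the same way: for eczema it reports a criterion of "at least one course of a potent topical steroid", a floor with no ceiling. An intended exclusion of the top tier is therefore unlikely. That is a fair account of intent, but the text still leaves the exclusion open, and two programmers could code it differently.

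Four stronger readings may tempt a reader, and the document does not support them.

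- *Ultra-high users are always classed as mild.* The consultation statement prevents this. Under OR a consultation alone makes the patient moderate/severe. Section 5.3's lists for nasal polyps and food allergy, which include a polypectomy or anaphylaxis at any time, make OR plausible.
- *The rule contradicts the rapid review on severity.* Appendix 13 uses the potent-steroid course to mark chronic eczema, and its source is a hand eczema study. It does not use it as a severity grade.
- *Severity contrasts are diluted because mild eczema is the reference category.* No section makes it one. Clusters are identified by Read codes (Section 5.2), with adrenaline prescribing added for anaphylaxis, and are untouched. The Phase 2 primary objective (Section 2.2) names demography, asthma severity, resource use and costs, not eczema severity.
- *Unlisted products add a large further error.* The protocol does not say that Appendix 6 is exhaustive or that unlisted products count as mild. That follows only by inference from the residual rule, and the document does not show how often such products are prescribed. Product lists may also be completed elsewhere. The gap is real but secondary.

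**Conclusion.** The point holds in a limited form. Section 5.3 and Appendix 6 do not map onto each other. Read as written, the severity rule is not monotone in potency: a patient treated only with an Ultra-high product ranks below a comparable High patient in one cell under each reading of the connector.

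This rests on two assumptions: that the upper end of the range is applied literally, and that no Moderate or High product was prescribed in the same year. If the range is read as medium or above, the Ultra-high fault disappears, while the lack of a rule for unlisted products remains. The number of patients is unknown. The effect is confined to the Phase 2 severity breakdown of atopic dermatitis. It should be corrected before Phase 2 because the text can give a wrong class and the repair is simple.

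**What to change.** 1. Restate the prescription criterion in Appendix 6 labels: *moderate, high or ultra-high potency*. The scale is then monotone under either connector.
2. In the same edit, state whether the consultation and prescription statements are joined by AND or OR. This choice decides whether a consultation alone makes atopic dermatitis moderate/severe, so it may move more patients than the Ultra-high wording does.
3. As a secondary step, assign a potency class to any prescribed topical steroid missing from Appendix 6 before the residual mild rule is applied, and name the source used. Section 6.7 cites the electronic British National Formulary only for filling gaps in drug prices, so the protocol does not yet name a source for these classes.

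The first two steps cost a line or two of protocol text. The third needs a review of the product list against the prescribing records. None needs new data.

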5.2 Identifying comorbidities of interest

The nine T2-type comorbidities of interest (atopic dermatitis; allergic rhinitis; chronic rhinosinusitis; nasal polyps; urticaria; allergic conjunctivitis; food allergy; eosinophilic oesophagitis; and anaphylaxis) will be identified by the presence of a Read code for the condition in the patient record. Anaphylaxis will also be identified by the prescription of adrenaline. Appendix 3 lists conditions where there are existing Read code definitions and those which will be developed during the study.

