Moderate/severe: A primary or secondary care consultation in the previous year. Three or more nasal corticosteroid in the previous year. Polypectomy at any time.

Urticaria

Active: A primary or secondary care consultation in the previous two years. Prescription of an oral antihistamine in the previous year.

Moderate/severe: A primary or secondary care consultation in the previous year. A double or greater dose of an oral antihistamine at any time prior to the index date.

Allergic Conjunctivitis

Active: A primary or secondary care consultation in the previous year. Prescription of any topical eye drop in the previous year.

Moderate/severe: A primary or secondary care consultation in the previous year. Two or more prescriptions of any topical eye drop in the previous year.

Food Allergy

Active: Always active.

Moderate/severe: A primary care consultation in the previous year. A secondary care consultation in the past two years. A prescription for adrenaline in the past 30 months (adrenaline has an 18-month shelf life). Anaphylaxis at any time.

Eosinophilic oesophagitis

Active: Always active (as long-term treatment required).

Moderate/severe: Always categorised as moderate/severe (differentiation not appropriate).

Anaphylaxis

Active: Always active (there is always a risk of a subsequent episode).

Moderate/severe: A secondary care consultation, ER attendance or hospital admission in the past year. A prescription for adrenaline in the past 30 months (adrenaline has an 18-month shelf life).

Sources

[1] How much of a topical agent should be prescribed for children of different sizes? Andrew A. Nelson, Alicia D. Miller, Alan B. Fleischer, Rajesh Balkrishnan, Steven R. FeldmaJ Dermatolog Treat. 2006; 17(4): 224–228.

[2] UpToDate (<https://www.uptodate.com/home>).

[3] Rapid reviews to identify comorbidity definitions used in other studies using routine patient data (see Appendices 13 and 14).

[5] Lucendo AJ, Arias Á, Molina-Infante J, Arias-González L. The role of endoscopy in eosinophilic esophagitis: from diagnosis to therapy. Expert Review of Gastroenterology & Hepatology. 2017; 11(12): 1135-1149.

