6.3 CONSORT chart

A CONSORT-type chart, describing the number and proportion of patients retained and excluded at each step of the inclusion/exclusion criteria will be generated for each study phase.

6.4 Demographic and clinical characteristics of patients at index date (phase 1 and 2)

Phase 1: The demographic and clinical characteristics at index date of patients included in the analysis will be tabulated: this will include the number and proportion of patients with each of the comorbidities of interest. For completeness, the number of patients with no comorbidities will also be reported. As it will not be possible to distinguish between inactive and active comorbidity and mild to moderate/severe comorbidity for all comorbidities of interest without linked HES data, this will be reported as the number of patients with active/inactive comorbidity.

Phase 2: A similar set of outputs will be produced for the second phase. In addition, the number and proportion of patients whose comorbidity is inactive, active, mild and

moderate/severe will be tabulated for each comorbidity using the primary care and linked HES data.

Patient characteristics at index date will be reported for the study population using the following conventions:

- Continuous variables will be summarised using descriptive statistics: n (non-missing sample size), percentage of non-missing, mean, standard deviation, median, inter-quartile range (25th and 75th percentile), maximum and minimum.
- For categorical measures, the frequency and percentages (based on the non-missing sample size) of observed levels will be reported.

Comorbidity prevalence will be estimated for each comorbidity cluster by dividing the number of patients in the cluster by the total number of patients eligible for inclusion in the study.

The ratio of observed to expected cases for each comorbidity cluster will be estimated by dividing the observed prevalence of the cluster by the expected prevalence of the cluster (the product of the prevalence of each individual disease in the cluster).

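### Allergic conjunctivitis is graded on eye drops of any kind, so drops prescribed for other eye conditions can misclassify its activity and severity in Phase 2

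*Protocol*

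**What the plan says.** Section 5.2 of the protocol states that the nine comorbidities "will be identified by the presence of a Read code for the condition in the patient record". It sets no time window, so a single code from decades ago qualifies.

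Section 5.3 then grades each comorbidity at the index date. For allergic conjunctivitis, each grade lists two criteria. The first, identical in both grades, is a consultation in the previous year. The second is a drug criterion: "Prescription of any topical eye drop in the previous year" for active and "Two or more prescriptions of any topical eye drop in the previous year" for moderate/severe. The text does not say whether the two criteria are alternatives or must both be met.

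The same section has a note on drugs with several indications. It is motivated by the fact that "some medications can be indicated for more than one of the comorbidities of interest", and its rule is that "the diagnosis recorded closest in time to the initiation of the medication will be taken as the indication".

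The grades are used in Phase 2. Under section 6.4 the numbers inactive, active, mild and "moderate/severe will be tabulated for each comorbidity using the primary care and linked HES data". Section 6.6 characterises the selected clusters by comorbidity severity and activity, among other variables.

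**The concern.** Eye drops are a route of administration, not a treatment class. The criterion as worded takes in products for glaucoma, dry eye and infection, none of which is evidence of allergic eye disease. Because the diagnosis may be old and remitted, the drug criterion has to carry much of the information about current disease, and here it is not specific to the disease.

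The other drug criteria in section 5.3 do name a class or agent. Allergic rhinitis uses "Prescription of a nasal corticosteroid in the previous year" and urticaria uses "Prescription of an oral antihistamine in the previous year". Chronic rhinosinusitis and nasal polyps also use nasal corticosteroids, atopic dermatitis uses topical corticosteroids graded by the potency table in Appendix 6, and food allergy and anaphylaxis use adrenaline. Allergic conjunctivitis is the exception.

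At stake are the Phase 2 tables of activity and severity for this comorbidity and the description of any cluster that contains it. If use of other eye treatments varies with age, the error would differ between age groups, and age is one of the variables by which section 6.6 describes the clusters.

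**Working it through.** The plan gives no figure to reproduce: section 6.1 lists only available patient counts. The check is a reading of the rules, followed by an illustration of size.

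**Step 1: the two readings.** Let C be a qualifying consultation in the previous year and D the number of eye-drop prescriptions in that year.

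- OR: active if C or D ≥ 1; moderate/severe if C or D ≥ 2.
- AND: active if C and D ≥ 1; moderate/severe if C and D ≥ 2.

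OR fits the rest of section 5.3 better. Food allergy has four separate moderate/severe criteria with different look-back periods, and nasal polyps adds past polypectomy. These read as alternative routes.

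**Step 2: what a non-allergy drop does.** Assume that the consultation must be for the eye condition.

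| Patient with a Read code of any date | OR | AND |
|---|---|---|
| Remitted, no consultation, one antibiotic drop | active | inactive |
| Remitted, no consultation, two or more glaucoma or lubricant drops | active, moderate/severe | inactive |
| Consultation, one anti-allergic and one antibiotic drop | moderate/severe by the consultation alone | moderate/severe only because of the antibiotic drop |

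Under OR the error falls on patients without a qualifying consultation, because a consultation already satisfies both grades. Under AND, drops alone reclassify nobody. The drop count is then the only thing separating moderate/severe from milder active disease, and a non-allergy drop can supply the second prescription.

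**Step 3: does the nearest-diagnosis rule catch this?** Glaucoma, dry eye and infective conjunctivitis are not among the nine comorbidities in section 3.1, and Appendix 3 plans no code lists for them. Read narrowly, the rule arbitrates among the nine and leaves these drops in. Read broadly, a coded glaucoma diagnosis near the first prescription would claim the drops. Drops issued for an eye complaint that was never coded would still count.

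**Step 4: scale, on assumptions only.** None of these inputs is in the documents. All results take the OR reading with no removal of drops by the nearest-diagnosis rule.

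*Active.* Let a be the share of ever-coded patients with current disease, all of them detected, and r the share of remitted patients given at least one non-allergy drop in the year. Labelled active = a + (1 − a)r, and false share = (1 − a)r / [a + (1 − a)r].

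- a = 20%, r = 5%: 0.20 + 0.80 × 0.05 = 0.24; false share 0.04/0.24 = 17%.
- a = 20%, r = 15%: 0.20 + 0.80 × 0.15 = 0.32; false share 0.12/0.32 = 38%.

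*Moderate/severe.* Let q be the share of remitted patients with two or more non-allergy drop prescriptions, and s the share of current patients who meet moderate/severe. False share = (1 − a)q / [(1 − a)q + a·s].

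- a = 40%, q = 2%, s = 60%: 0.012/(0.012 + 0.240) = 5%.
- a = 20%, q = 5%, s = 60%: 0.040/(0.040 + 0.120) = 25%.
- a = 10%, q = 10%, s = 30%: 0.090/(0.090 + 0.030) = 75%.

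The range is so wide that it shows only that the error could be material. It does not estimate it.

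**The case against.** The strongest reply has three parts.

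First, the consultation and prescription criteria may be joint. A reader might infer that glaucoma drops simply turn an old diagnosis into current moderate/severe disease. The protocol does not support that as a flat statement: it holds only if a prescription alone suffices, which is never said. This stands, and the point is conditional for that reason. The AND reading does not clear the definition, however, because the severity threshold still counts irrelevant products.

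Second, the operative sentence of the nearest-diagnosis rule is worded without limit and could send drops to a coded glaucoma or infection diagnosis. This stands in part. The reading is possible, but the rule is introduced for overlap among the nine, it does not amend the unrestricted drop wording, and it cannot help where the other eye complaint is uncoded.

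Third, the broad wording may be deliberate, to avoid missing patients, and a closed list of antihistamine and mast-cell-stabilising drops could lose more severe allergic eye disease treated with other anti-inflammatory drops. This stands as a limit on the fix. It does not justify counting glaucoma, lubricant or anti-infective products.

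**Conclusion.** The definition is too loose as written and should be tightened before Phase 2. Under OR, non-allergy drops can label a remitted diagnosis active or moderate/severe; under AND, they can still inflate the moderate/severe count.

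The reach is narrow. Comorbidities are identified by Read code, so Phase 1 prevalence, observed/expected ratios and cluster selection do not depend on this line, and the asthma-related resource-use counts in section 5.4 do not either. What is affected is the Phase 2 activity and severity categories of one comorbidity of nine. The sensitivity analysis in section 6.9 concerns record length and would not reveal the problem.

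The size cannot be derived from the documents. The 17% to 38% for active and the 5% to 75% for moderate/severe are illustrations under assumed inputs.

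A reader might also infer that the age analyses would show allergic conjunctivitis persisting or worsening in older patients. That goes too far. Each patient is classified once, at the index date, so only differences between age groups can appear. That the error rises with age is plausible, but no figure in the documents supports it.

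**What to change.** Make three changes in section 5.3:

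1. In both the active and the moderate/severe definitions, replace the unrestricted eye-drop criterion with a prespecified code list of eye preparations used for allergic eye disease, excluding glaucoma, lubricant and anti-infective products.
2. Attribute non-specific products, such as anti-inflammatory drops, by the nearest-diagnosis rule, and extend that rule explicitly to eye diagnoses outside the nine comorbidities.
3. State whether the consultation and prescription criteria are joined by AND or by OR.

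The cost is one extra product code list, which can be built alongside the allergic conjunctivitis Read code list that Appendix 3 still has to develop, plus a few edited lines. Extending the rule also means recognising other coded eye diagnoses. The downside is that a few allergic patients treated only with non-specific drops will no longer be counted by prescription. Whether a consultation still brings them in depends on the answer to the third change.
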